### Assessment of Intensity

The investigator will make an assessment of intensity for each AE and SAE reported during the study and assign it to 1 of the following categories, which are based on the Division of AIDS (DAIDS) Table for Grading the Severity of Adult and Pediatric Adverse Events, version 2.1 (July 2017):

GRADE	Clinical Description of Severity
1	MILD adverse event
2	MODERATE adverse event
3	SEVERE adverse event
4	POTENTIALLY LIFE-THREATENING event
5	DEATH RELATED TO adverse event

An event is defined as “serious” when it meets at least 1 of the predefined outcomes as described in the definition of an SAE, NOT when it is rated as severe.

### Assessment of Causality

- The investigator is obligated to assess the relationship between study intervention and each occurrence of each AE or SAE. The investigator will use clinical judgment to determine the relationship.
- A “reasonable possibility” of a relationship conveys that there are facts, evidence, and/or arguments to suggest a causal relationship, rather than a relationship cannot be ruled out.
- Alternative causes, such as underlying disease(s), concomitant therapy, and other risk factors, as well as the temporal relationship of the event to study intervention administration, will be considered and investigated.
- The investigator will also consult the IB and/or product information, for marketed products, in their assessment.

- For each AE or SAE, the investigator **must** document in the medical notes that they have reviewed the AE or SAE and have provided an assessment of causality.
- There may be situations in which an SAE has occurred and the investigator has minimal information to include in the initial report to the sponsor. However, **it is very important that the investigator always make an assessment of causality for every event before the initial transmission of the SAE data to the sponsor.**
- The investigator may change their opinion of causality in light of follow-up information and send an SAE follow-up report with the updated causality assessment.
- The causality assessment is one of the criteria used when determining regulatory reporting requirements.
- If the investigator does not know whether or not the study intervention caused the event, then the event will be handled as “related to study intervention” for reporting purposes, as defined by the sponsor. In addition, if the investigator determines that an SAE is associated with study procedures, the investigator must record this causal relationship in the source documents and CRF, and report such an assessment in the dedicated section of the PSSA and in accordance with the SAE reporting requirements.

#### Follow-Up of AEs and SAEs

- The investigator is obligated to perform or arrange for the conduct of supplemental measurements and/or evaluations, as medically indicated or as requested by the sponsor, to elucidate the nature and/or causality of the AE or SAE as fully as possible. This may include additional laboratory tests or investigations, histopathological examinations, or consultation with other healthcare providers.
- If a participant dies during participation in the study or during a recognized follow-up period, the investigator will provide Pfizer Safety with a copy of any postmortem findings, including histopathology.
- New or updated information will be recorded in the originally submitted documents.
- The investigator will submit any updated SAE data to the sponsor within 24 hours of receipt of the information.

#### 10.3.4. Reporting of SAEs

##### SAE Reporting to Pfizer Safety via an Electronic DCT

- The primary mechanism for reporting an SAE to Pfizer Safety will be the electronic DCT.
- If the electronic system is unavailable, then the site will use the paper SAE DCT (see next section) to report the event within 24 hours.
- The site will enter the SAE data into the electronic DCT (eg, eSAE or PSSA) or paper form (as applicable) as soon as the data become available.
- After the study is completed at a given site, the electronic DCT will be taken off-line to prevent the entry of new data or changes to existing data.
- If a site receives a report of a new SAE from a study participant or receives updated data on a previously reported SAE after the electronic DCT has been taken off-line, then the site can report this information on a paper SAE form (see next section) or to Pfizer Safety by telephone.

##### SAE Reporting to Pfizer Safety via the CT SAE Report Form

- Facsimile transmission of the CT SAE Report Form is the preferred method to transmit this information to Pfizer Safety.
- In circumstances when the facsimile is not working, an alternative method should be used, eg, secured (Transport Layer Security) or password-protected email. If none of these methods can be used, notification by telephone is acceptable with a copy of the CT SAE Report Form sent by overnight mail or courier service.
- Initial notification via telephone does not replace the need for the investigator to complete and sign the CT SAE Report Form pages within the designated reporting time frames.

## **10.4. Appendix 4: Contraceptive and Barrier Guidance**

### **10.4.1. Male Participant Reproductive Inclusion Criteria**

No contraception methods are required for male participants in this study, as the calculated safety margin is  $\geq 100$ -fold between the estimated maternal exposure due to seminal transfer and the NOAEL for serious manifestations of developmental toxicity in nonclinical studies.

### **10.4.2. Female Participant Reproductive Inclusion Criteria**

The criteria below are part of Inclusion Criterion 1 (Age and Sex; Section 5.1) and specify the reproductive requirements for including female participants. Refer to Section 10.4.4 for a complete list of contraceptive methods permitted in the study.

A female participant is eligible to participate if she is not pregnant or breastfeeding and at least 1 of the following conditions applies:

- Is not a WOCBP (see definition in Section 10.4.3).

OR

- Is a WOCBP and agrees to use an acceptable contraceptive method: intrauterine device (IUD), dual barrier method, partner vasectomy, or abstinence, during the intervention period and for at least 28 days after the last dose of study intervention, which corresponds to the time needed to eliminate any reproductive safety risk of the study intervention(s). The investigator should evaluate the effectiveness of the contraceptive method in relationship to the first dose of study intervention.

Because ritonavir may reduce the effect of estradiol-containing contraceptives when agents are co-administered, a barrier method or other nonhormonal method of contraception must also be used if the participant is using estradiol-containing contraceptives during the 5 days of PF-07321332 (nirmatrelvir)/ritonavir treatment and until one menstrual cycle after stopping study intervention.

The investigator is responsible for review of medical history, menstrual history, and recent sexual activity to decrease the risk for inclusion of a woman with an early undetected pregnancy.

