#### **4.2.1. Choice of Contraception/Barrier Requirements**

Human reproductive safety data are not available for PF-07321332 (nirmatrelvir)/ritonavir, but there is no suspicion of human teratogenicity based on the intended pharmacology of the compound. Therefore, the use of a highly effective method of contraception is required for WOCBP (see [Appendix 4](#)).

The given study population reproductive capability is limited and the risk of reproductive safety may be minimized because of this. The investigator should determine the participant's potential for becoming pregnant. For women who met Inclusion Criterion 1 in section [5.1](#) per the investigator's assessment, an acceptable hormone based contraception should be used during the participant's time in the study as described in Section [10.4.4](#).

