### Age and Sex:

1. Participants  $\geq 18$  years of age (or the minimum country specific age of consent if  $>18$ ) at the time of the Screening Visit.
  - WOCBP may be enrolled.
  - WOCBP must agree to use an effective method of contraception described in Section 5.3. See [Appendix 4](#) for reproductive criteria for male and female participants.

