### **5.3. Lifestyle Considerations**

#### **5.3.1. Contraception**

No contraception methods are required for male participants in this study (see [Appendix 4, Section 10.4.1](#)).

The investigator or their designee, in consultation with the participant, will confirm that the participant is utilizing an appropriate method of contraception for the individual participant from the permitted list of contraception methods (see [Appendix 4, Section 10.4.4](#)) and will confirm that the participant has been instructed in its consistent and correct use. At time points indicated in the [SoA](#), the investigator or designee will inform the participant of the need to use highly effective contraception consistently and correctly and document the conversation and the participant's affirmation in the participant's chart. Participants need to affirm their consistent and correct use of at least 1 of the selected methods of contraception, considering that their risk for pregnancy may have changed since the last visit.

In addition, the investigator or designee will instruct the participant to call immediately if the selected contraception method is discontinued and document the requirement to use an alternate protocol-specified method, including if the participant will no longer use abstinence as the selected contraception method, or if pregnancy is known or suspected in the participant or partner.

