### **10.4.3. Woman of Childbearing Potential**

A woman is considered fertile following menarche and until becoming postmenopausal unless permanently sterile (see below).

If fertility is unclear (eg, amenorrhea in adolescents or athletes) and a menstrual cycle cannot be confirmed before the first dose of study intervention, additional evaluation should be considered.

Women in the following categories are not considered WOCBP:

1. Premenopausal female with 1 of the following:

- Documented hysterectomy;
- Documented bilateral salpingectomy;
- Documented bilateral oophorectomy.

For individuals with permanent infertility due to a medical cause other than the above (eg, mullerian agenesis, androgen insensitivity), investigator discretion should be applied to determining study entry.

Note: Documentation for any of the above categories can come from the site personnel's review of the participant's medical records, medical examination, or medical history interview. The method of documentation should be recorded in the participant's medical record for the study.

2. Postmenopausal female:

- A postmenopausal state is defined as no menses for 12 months without an alternative medical cause. In addition:
  - A female on HRT and whose menopausal status is in doubt will be required to use one of the highly effective non-estrogen hormonal contraception methods if she wishes to continue her HRT during the study. Otherwise, she must discontinue HRT to allow confirmation of postmenopausal status before study enrollment.
  - A negative urine pregnancy test must be confirmed at screening or Day 1 prior to dispensing treatment for all women unless they are 50 years or older with no menses for 12 months.

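### Section 10.4.2 accepts dual barrier as sufficient contraception for a WOCBP, although Sections 4.2.1 and 5.3.1 call for a highly effective method and 10.4.4 labels barrier methods not highly effective

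*Protocol*

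**What the plan says.** The rule is spread over several places in the protocol.

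- **Inclusion Criterion 1 (synopsis and Section 5.1):** "WOCBP must agree to use an effective method of contraception". The criterion then sends the reader both to Section 5.3 and to Appendix 4.
- **Section 4.2.1:** "the use of a highly effective method of contraception is required for WOCBP". The next paragraph says that, for women meeting Inclusion Criterion 1, "an acceptable hormone based contraception should be used during the participant's time in the study".
- **Section 5.3.1:** the investigator confirms a suitable method "from the permitted list of contraception methods", citing 10.4.4, and at the visits in the Schedule of Activities must "inform the participant of the need to use highly effective contraception consistently and correctly".
- **Section 10.4.2, declared to be part of Inclusion Criterion 1:** a woman qualifies if she "Is a WOCBP and agrees to use an acceptable contraceptive method: intrauterine device (IUD), dual barrier method, partner vasectomy, or abstinence", through treatment and for at least 28 days after the last dose. The same section says: "Refer to Section 10.4.4 for a complete list of contraceptive methods permitted in the study". A further paragraph requires users of estradiol-containing contraceptives to add a barrier or other nonhormonal method.
- **Section 10.4.4:** five numbered methods under a heading that calls them highly effective, then sexual abstinence as item 6. An asterisked note on barrier methods follows. It marks them as not highly effective and names double-barrier combinations among them.

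**The concern.** An eligibility criterion should give one answer for each participant. Here the answer for a woman using only dual barrier depends on which of the criterion's two references the site follows. Appendix 4, through 10.4.2, admits her. Section 5.3 tells her to use highly effective contraception, which the protocol's own classification says dual barrier is not.

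Two things are at stake. Sites could decide differently on the same facts, or could enrol a woman below the standard that 4.2.1 sets. That standard was chosen after noting that human reproductive safety data are not available. The conflict also persists after enrolment. The contraception check in the Schedule of Activities is marked at every visit and points to 5.3.1, so a woman admitted under 10.4.2 would keep being told to meet a standard that her method does not meet.

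**Working it through.** No arithmetic decides this point, so the check sets the texts side by side. The test case is a WOCBP whose sole method is dual barrier.

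| Place in the protocol | Standard for a WOCBP | Dual barrier alone |
|---|---|---|
| Synopsis and 5.1, Criterion 1 | effective; defers to 5.3 and Appendix 4 | not settled here |
| 4.2.1, first paragraph | highly effective, required | does not meet it |
| 4.2.1, second paragraph | acceptable and hormone-based, worded as *should* | does not meet it |
| 5.3.1 | method from the 10.4.4 list; participant told to use highly effective contraception | does not meet the highly effective standard |
| 10.4.2 | acceptable; any one of four named methods | meets it |
| 10.4.4 | six numbered methods; barrier methods in a note | labelled not highly effective |

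**Step 1: does 10.4.2 really accept dual barrier by itself?** The word *alone* is not used. But the four methods are alternatives joined by *or*, and agreeing to one of them satisfies the condition. Dual barrier is therefore sufficient under that text.

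**Step 2: is dual barrier highly effective under this protocol?** Section 10.4.4 answers directly. Its note gives barrier methods as a group the label not highly effective, and double-barrier is one of the listed examples.

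**Step 3: where is highly effective actually required?** Section 4.2.1 states it as a requirement. Section 5.3.1 states it as what participants must be told. Section 10.4.4 contains no sentence of requirement; it contributes the list and the label. Section 10.4.3 uses the same standard for one subgroup: a woman on HRT whose menopausal status is in doubt is "required to use one of the highly effective non-estrogen hormonal contraception methods if she wishes to continue her HRT".

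**Step 4: follow Criterion 1 both ways.** Through 5.3, the path is 5.3.1 and then 10.4.4, and the woman falls below the standard. Through Appendix 4, the path is 10.4.2, and she is eligible. Section 10.4.2 is also at odds with its own pointer: it calls 10.4.4 complete, yet dual barrier is not among the numbered methods there.

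**Step 5: the period affected.** The last dose is on Day 5, and 5 + 28 = 33, so contraception is required to at least Day 33. The conflict does not alter that period.

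**The case against.** The best defence is that 10.4.4 does mention double-barrier, and introduces its contents as methods appropriate for the study. The note on barrier methods is badly formed, and its asterisk has no visible anchor. On the narrow question of whether dual barrier appears somewhere in the permitted list, a site could argue that it does. That much stands. It does not help on the standard itself, because the not highly effective label is unambiguous and 4.2.1 and 5.3.1 call for highly effective.

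It can also be said that the direction of the correction is not fully dictated by the text. Section 4.2.1 is itself uneven, with its sentence on hormone-based methods, and Criterion 1 says only effective. That is fair. The sponsor could have meant dual barrier to qualify, but would then have to lower the standard in 4.2.1 and 5.3.1.

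Four stronger inferences are tempting, and the documents do not support them.

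- *Section 10.4.2 ignores hormonal contraception.* That is true only of its four-method list. Its next paragraph deals with estradiol-containing contraceptives.
- *The methods missing from 10.4.2, such as the progestogen-only implant or tubal occlusion, are a second contradiction.* They are reached through that section's own reference to 10.4.4.
- *Section 10.4.4 permits barrier methods only together with abstinence.* The note speaks of use alongside item 6, but the word *only* is not there, and the sentence is too garbled to carry a firm rule.
- *Sites have no way out because waivers are barred.* Sections 5 and 8.1 forbid waiving criteria. They do not stop a site from asking the sponsor which text governs.

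**Conclusion.** The point holds. Section 10.4.2 admits a woman on dual barrier alone, and that method falls below the standard stated in 4.2.1 and 5.3.1. This is an error in an operative eligibility and safety rule, so it should be corrected.

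Its size is minor. Dosing lasts 5 days, and 4.2.1 reports no suspicion of human teratogenicity. Pregnancy is tested before treatment, at Day 34 or early termination, after a missed cycle during active treatment, and whenever it is suspected. Section 10.4.2 also asks the investigator to evaluate the method's effectiveness in relation to the first dose. The protocol does not give the number of WOCBP; 4.2.1 says only that reproductive capability in this population is limited, so few are likely. No endpoint, sample size or analysis changes.

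The conclusion rests on reading *or* in 10.4.2 in its ordinary sense. The preferred direction of the fix also assumes that the highly effective standard in 4.2.1 is what the sponsor intends.

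**What to change.** Make 10.4.4 the single governing list, at the next amendment:

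1. In 10.4.2, replace the four-method list with *a highly effective contraceptive method listed in Section 10.4.4*, and keep the 28-day period.
2. In 10.4.4, rewrite the barrier note to say that barrier methods may be added to a listed method but do not qualify alone.
3. In 4.2.1, replace the phrase on acceptable hormone-based contraception with *a highly effective method of contraception*. In 5.1 and the synopsis, change *effective* to *highly effective*.
4. In the estradiol paragraph of 10.4.2, state that estradiol-containing contraceptives, with or without a barrier, do not qualify unless a method listed in 10.4.4 is also used. Without this step, the paragraph would go on regulating women whom the governing list does not admit.

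If the sponsor does want dual barrier to qualify, the alternative is to lower the standard in 4.2.1 and 5.3.1 and list dual barrier in 10.4.4 as a qualifying method.

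The preferred fix adds no visit, procedure or analysis. Its cost is that a WOCBP willing to use only dual barrier becomes ineligible. Step 4 has the same effect for a woman who would rely only on an estradiol-containing contraceptive plus a barrier.

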### **10.4.3. Woman of Childbearing Potential**

A woman is considered fertile following menarche and until becoming postmenopausal unless permanently sterile (see below).

If fertility is unclear (eg, amenorrhea in adolescents or athletes) and a menstrual cycle cannot be confirmed before the first dose of study intervention, additional evaluation should be considered.

Women in the following categories are not considered WOCBP:

1. Premenopausal female with 1 of the following:

- Documented hysterectomy;
- Documented bilateral salpingectomy;
- Documented bilateral oophorectomy.

For individuals with permanent infertility due to a medical cause other than the above (eg, mullerian agenesis, androgen insensitivity), investigator discretion should be applied to determining study entry.

Note: Documentation for any of the above categories can come from the site personnel's review of the participant's medical records, medical examination, or medical history interview. The method of documentation should be recorded in the participant's medical record for the study.

2. Postmenopausal female:

- A postmenopausal state is defined as no menses for 12 months without an alternative medical cause. In addition:
  - A female on HRT and whose menopausal status is in doubt will be required to use one of the highly effective non-estrogen hormonal contraception methods if she wishes to continue her HRT during the study. Otherwise, she must discontinue HRT to allow confirmation of postmenopausal status before study enrollment.
  - A negative urine pregnancy test must be confirmed at screening or Day 1 prior to dispensing treatment for all women unless they are 50 years or older with no menses for 12 months.

#### **10.4.4. Contraception Methods**

Contraceptive use by men or women should be consistent with local availability/regulations regarding the use of contraceptive methods for those participating in clinical trials.

The following contraceptive methods are appropriate for this study:

##### Highly Effective Methods That Have Low User Dependency

1. Implantable progestogen-only hormone contraception associated with inhibition of ovulation.
2. Intrauterine device.

3. Intrauterine hormone-releasing system.
4. Bilateral tubal occlusion.
5. Vasectomized partner:
  - Vasectomized partner is a highly effective contraceptive method provided that the partner is the sole sexual partner of the WOCBP and the absence of sperm has been confirmed. If not, an additional highly effective method of contraception should be used. The spermatogenesis cycle is approximately 90 days.

#### Sexual Abstinence

6. Sexual abstinence is considered a highly effective method only if defined as refraining from heterosexual intercourse during the entire period of risk associated with the study intervention. The reliability of sexual abstinence needs to be evaluated in relation to the duration of the study and the preferred and usual lifestyle of the participant.

\* Acceptable barrier methods (not highly effective) may be used concomitantly with option 6 above for the study include any of the following:

- Male or female condom, with or without spermicide;
- Cervical cap, diaphragm, or sponge with spermicide;
- A combination of male condom with either cervical cap, diaphragm, or sponge with spermicide (double-barrier methods).

## 10.5. Appendix 5: Genetics

### Use/Analysis of DNA

- Genetic variation may impact a participant's response to study intervention, susceptibility to, and severity and progression of disease. Therefore, where local regulations and IRBs/ECs allow, a blood sample will be collected for DNA analysis.
- The scope of the genetic research may be narrow (eg, 1 or more candidate genes) or broad (eg, the entire genome), as appropriate to the scientific question under investigation.
- The samples may be analyzed as part of a multistudy assessment of genetic factors involved in the response to PF-07321332 (nirmatrelvir)/ritonavir or study interventions of this class to understand treatments for the disease(s) under study or the disease(s) themselves.
- The results of genetic analyses may be reported in the CSR or in a separate study summary, or may be used for internal decision making without being included in a study report.
- The sponsor will store the DNA samples in a secure storage space with adequate measures to protect confidentiality.
- The samples will be retained as indicated:
  - Retained samples will be stored indefinitely or for another period as per local requirements.
  - Participants may withdraw their consent for the storage and/or use of their Retained Research Samples at any time by making a request to the investigator; in this case, any remaining material will be destroyed. Data already generated from the samples will be retained to protect the integrity of existing analyses.
  - Samples for genetic research will be labeled with a code. The key between the code and the participant's personally identifying information (eg, name, address) will be held securely at the study site.

